### 9.3 POPULATIONS FOR ANALYSES

**PK analysis Population:** All participants with at least 1 PK sample will be included in the population PK analysis.

**Intent-to-Treat (ITT) Population:** This population includes all enrolled participants. Analysis of the ITT population will be used for all non-PK analyses.

**Safety Population:** This analysis population includes all enrolled participants who received at least one dose of study treatment.

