## 9.4 STATISTICAL ANALYSES

### 9.4.1 GENERAL APPROACH

Following finalization of the Protocol, but prior to 25% enrollment, a Statistical Analysis Plan (SAP) will be issued as a separate document, which will provide detailed analytical plans for the set of analyses outlined below. All statistical analyses will be conducted following the statistical principles for clinical trials as specified in International Conference on Harmonization Statistical Principles for Clinical Trials (ICH Topic E9). Any deviations from the planned analyses will be described and justified in the final integrated clinical study report. All study data and summary tables will be presented overall and by study sites.

Descriptive statistics for continuous data will be summarized using mean and standard deviation or median and interquartile range, as appropriate. Categorical data will be summarized using frequency and percent. Any outliers detected during data review will be investigated and methods for handling outliers or data transformation will be defined in the SAP.

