#### 9.4.5 SAFETY ANALYSES

All AEs recorded during the study period will be coded with Medical Dictionary for Regulatory Activities (MedDRA) Version March 2018. All participants enrolled in the study will be evaluated for safety. Summaries of AE will be tabulated for the following types:

- Number (%) of participants with any AE or AR
- Number (%) of participants with any SAE or SAR
- Number (%) of participants withdrawn from treatment due to AE

All summaries will be reported overall and by study site. Additional analyses and summaries may be derived if deemed appropriate and will be further described in the SAP.

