#### 9.4.6 BASELINE DESCRIPTIVE STATISTICS

Baseline and demographic characteristics will be summarized overall and by study site. Summary statistics will be applied for both continuous and categorical variables. For continuous measures, descriptive measures will include number of non-missing values, mean, standard deviation, median, minimum, and maximum. For categorical variables, descriptive statistics will include frequency counts and percentages by category.

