#### 9.4.9 TABULATION OF INDIVIDUAL PARTICIPANT DATA

A detailed description of participant disposition will be provided. The number of enrolled participants will be tabulated overall and by study site and presented as counts and percentages. Additionally, the number of participants either completing or discontinuing the study will be summarized using counts and percentages.

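### The adverse-event denominator is stated inconsistently and, as a separate point, no safety, baseline or discontinuation table is committed to by randomized cohort

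*Combined protocol and SAP*

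**What the plan says.** **Analysis set.** Section 9.4.5 says: "All participants enrolled in the study will be evaluated for safety". Section 9.3 defines the ITT population as everyone enrolled and adds: "Analysis of the ITT population will be used for all non-PK analyses". The same section defines a Safety Population: "This analysis population includes all enrolled participants who received at least one dose of study treatment". No sentence ties that Safety Population to the adverse-event tables in 9.4.5.

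**Enrolment.** Section 8.1.1.1 (Screening Visit) makes a child enrolled once consent and assent are obtained. That precedes the screening laboratory results, the run-in and randomization. Section 8.3.5 has adverse events documented from consent onward.

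**Table layout.** The general rule in 9.4.1 is: "All study data and summary tables will be presented overall and by study sites". For safety, 9.4.5 repeats it: "All summaries will be reported overall and by study site". For baseline, 9.4.6 says: "Baseline and demographic characteristics will be summarized overall and by study site". In 9.4.9, enrolled counts are given overall and by site, and then "the number of participants either completing or discontinuing the study will be summarized using counts and percentages", with no split named.

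**Deferral.** Section 9.4.1 says that "a Statistical Analysis Plan (SAP) will be issued as a separate document, which will provide detailed analytical plans". Section 9.4.5 adds that further safety summaries may be derived where judged appropriate and would be described in that SAP. The separate SAP is not part of the text available here.

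**The concern.** Section 3 lists safety and tolerability of oral vitamin D3 as an objective, and Section 2.1 says the study is to supply dosing and safety data for a later trial. Two things are needed for that: a fixed denominator, and a view of events by regimen. The regimens run from 600 IU/day to 10,000 IU/day plus a 50,000 IU load.

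On the denominator, two sentences point to everyone who consented and one definition points to those dosed. Children who consented and never took a capsule cannot inform tolerability, but they would lower every percentage if counted.

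On layout, the text asks for site columns and is silent on the groups that were randomized. The protocol does name regimens where it wants regimen-level output: 25(OH)D response in 9.4.3, 9.4.4 and 9.5. An overall figure does not describe the tolerability of any one regimen, including the Part 2 regimen, which Section 4.3 says was not one of the Part 1 arms.

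**Working it through.** **Inputs**
- Enrolment maxima: 150 for Part 1 and 171 for Part 2 (Section 4.1); total 321 (Section 5.5).
- Randomization maxima: 50 for Part 1 and 63 for Part 2 (Section 4.1). The summary in Section 1 still shows about 107 randomized; the maxima in 4.1 are used here.
- Allocation: 1:1:1:1 in Part 1 and 2:1 in Part 2 (Sections 4.1 and 9.2).
- Network size: 17 state awarded sites (Section 10.1.5). The number that randomize is not given.

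**Step 1. Reproduce the plan's total.** 150 + 171 = 321, which matches Section 5.5.

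**Step 2. The two denominators.** All enrolled: 321. Dosed: at most the number randomized, 50 + 63 = 113. The difference is 321 − 113 = 208 children who consented but were never randomized, if both maxima are reached.

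**Step 3. Effect on a percentage.** For a fixed number of affected children, all of them dosed, the ratio of the two percentages is enrolled ÷ dosed. Planned enrolment is a ceiling, so two lower enrolments are shown as assumptions.

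| Enrolled | Ratio to 113 | 10 affected children, all-enrolled set | 10 affected children, dosed set |
|---|---|---|---|
| 321 (planned maximum) | 321/113 = 2.8 | 10/321 = 3.1% | 10/113 = 8.8% |
| 226 (assumed) | 226/113 = 2.0 | 10/226 = 4.4% | 8.8% |
| 150 (assumed) | 150/113 = 1.3 | 10/150 = 6.7% | 8.8% |

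The count of 10 is illustrative; the ratio does not depend on it.

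**Step 4. What each section commits to.**

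| Table | Section | Splits named | Cohort named? |
|---|---|---|---|
| All study data and summaries | 9.4.1 | overall, site | no |
| AE, SAE, withdrawal from treatment due to AE | 9.4.5 | overall, site | no |
| Baseline and demographics | 9.4.6 | overall, site | no |
| Completing or discontinuing | 9.4.9 | none, so the 9.4.1 rule applies | no |
| 25(OH)D response | 9.4.3, 9.4.4, 9.5 | regimen or group | yes |

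**Step 5. Cell sizes if cohort columns are added.** Part 1: 50/4 = 12.5, so about 12 to 13 per cohort, assuming an even split. Table 2 shows 4 to 8 per cohort, but Section 4.1 reports 50 randomized. Part 2: 63 × 2/3 = 42 in Cohort A and 63 × 1/3 = 21 in Cohort B. Cohort A is then 42/113 = 37% of those randomized, so an overall safety column would be mostly other regimens.

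**Step 6. Compare with the site cells already planned.** 113/17 = 6.6 children per site if all 17 network sites randomize, and 113/10 = 11.3 if 10 do (assumed). Site cells would average no more than the smallest cohort cells in either case.

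**The case against.** The strongest reply on layout is that it cannot be settled from the protocol. Detailed plans are left to a separate SAP, 9.4.5 has its own deferral for extra safety summaries, and the word overall may mean only all sites together. That stands as a limit on the conclusion. It does not remove the point, because the 9.4.5 deferral is discretionary and commits to no cohort column.

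On the denominator, the reply is that a defined Safety Population would have no purpose if the general ITT sentence overrode it, and that evaluating all enrolled may mean only collecting events from consent. The row for withdrawal from treatment can apply only to treated children. The protocol also uses enrolment loosely: 9.4.7 speaks of enrolment at the new dose. These are fair readings, and the intended denominator may well be the dosed set. But 8.1.1.1 defines enrolment at consent, 4.1 gives separate enrolment and randomization targets, and nothing links the Safety Population to the AE tables. The ambiguity remains.

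The consequence is also limited. Individual halting rules (7.1), DSMB and medical-monitor review (10.1.6) and the use of safety data in choosing the Part 2 dose (4.3) all operate during the trial. They do not fix what the final tables show.

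Small cohort cells are a real drawback, but the site cells already planned are no larger on average.

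**Conclusion.** Both points hold, and they are independent: the denominator has no bearing on whether cohort columns exist.

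1. The denominator is inconsistent as written. At the planned maxima the choice is 321 or 113, up to a 2.8-fold difference in any AE percentage. This assumes that both maxima are reached and that enrolled means consented.
2. The protocol text commits to no safety, baseline or discontinuation table by randomized regimen. This is conditional on the separate SAP not supplying one.

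A reader might infer that the plan intends to merge 600 IU/day with the high-dose regimens. The text does not say so; it is silent on cohort. A reader might also infer that reported AE rates will be diluted to about a third of their true size. That needs the all-enrolled reading and full enrolment of 321 together; there is no dilution if the Safety Population is used.

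No hypothesis test, sample size or primary result is affected. The points should be settled before the final tables are programmed.

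**What to change.** **Denominator.** In 9.4.5, state that AE tables use the Safety Population of 9.3. In 9.3, exempt safety from the sentence assigning the ITT set to all non-PK analyses. List events in consented but undosed children separately, so that nothing recorded from consent is lost.

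**Layout.** In 9.4.1, 9.4.5 and 9.4.6, and for the completing and discontinuing counts in 9.4.9, add a split by randomized cohort (1, 2, 3, 4, A, B), as descriptive counts and percentages (usual summary statistics for continuous baseline measures) without tests. Enrolled and screen-failure counts can stay overall and by site, because enrolment precedes randomization. If the SAP already specifies cohort tables, a cross-reference in these sections is enough.

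Exact confidence intervals, and whether the two 600 IU/day groups (Cohorts 4 and B) are shown apart or combined, are optional.

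**Cost.** Wording in 9.3 and four parts of 9.4, plus table columns. Cohort assignment and adverse events are already recorded for each child, so no new data are needed. The downside is small cells: about 12 to 13 per Part 1 cohort, 42 in A and 21 in B. The cohort columns would reveal only large differences and should be read descriptively.

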#### 9.4.6 BASELINE DESCRIPTIVE STATISTICS

Baseline and demographic characteristics will be summarized overall and by study site. Summary statistics will be applied for both continuous and categorical variables. For continuous measures, descriptive measures will include number of non-missing values, mean, standard deviation, median, minimum, and maximum. For categorical variables, descriptive statistics will include frequency counts and percentages by category.

#### 9.4.7 PLANNED INTERIM ANALYSES

An interim PK analysis was performed after a minimum of 16 participants (at least 4 in each arm) completed PK sampling at Week 20 (visit 7) in Part 1 of the study. The interim PK analysis provided an optimal dosing regimen for Part 2.

Results of the Part 1 analysis were presented to the DSMB along with the recommended new dose. Enrollments at the new dose will begin after DSMB approval.

#### 9.4.8 SUBGROUP ANALYSES

Minimal subgroup analyses will be performed.

#### 9.4.9 TABULATION OF INDIVIDUAL PARTICIPANT DATA

A detailed description of participant disposition will be provided. The number of enrolled participants will be tabulated overall and by study site and presented as counts and percentages. Additionally, the number of participants either completing or discontinuing the study will be summarized using counts and percentages.

#### 9.4.10 EXPLORATORY ANALYSES

At each study visit, ACT (or c-ACT) and ASDs will be computed to monitor asthma control. The presence and number of severe asthma exacerbations (as defined by the need for oral or parenteral corticosteroids), unscheduled asthma-related healthcare utilizations, and asthma-related hospitalizations will be collected. General estimating equations will be used to assess changes in the number of exacerbations, ASDs and the ACT (or c-ACT) score over time.

Baseline and 16-week inflammatory biomarkers (leptin plus TNF $\alpha$ , IL-2, IL-6, IL-10 and IL-17 (cytokine panel)) will be collected to assess changes on vitamin D supplementation. Participants who opt for venipuncture for vitamin D levels (rather than fingerstick) will have blood drawn for inflammatory markers at more times. Total 25(OH)D, changes in 25(OH)D, changes in individual biomarkers, and asthma outcomes will be explored.

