### 5.2 EXCLUSION CRITERIA

An individual who meets any of the following exclusion criteria will be excluded from participation in the study:

- Known diseases of calcium metabolism or the parathyroid
- History of renal insufficiency or kidney stones
- Known liver failure or history of abnormal liver function which is deemed by the site investigator to be clinically significant
- History of Williams syndrome, sarcoidosis, or granulomatous disease
- Active tuberculosis

- Spot urine calcium/creatinine ratio greater than 0.37 on 2 consecutive visits. If the ratio is greater than 0.37 on the first visit, this test must be repeated once - following adequate hydration, within 2 business days of the study team being notified of the initial lab results.
- Clinical evidence of rickets
- Taking supplemental vitamin D greater than 1000 IU per day
- Administration of an excluded medication (systemic glucocorticoids, drugs affecting calcium metabolism, drug affecting fat absorption) within 30 days prior to study enrollment – at screening (Visit 1) or at any time during the run-in period.
- Other medical issues that in the opinion of the investigator put the participant at risk or affect results of the study (e.g., fat malabsorption, cystic fibrosis, chronic lung disease of prematurity, congenital heart disease). Type 2 diabetes is not an exclusion criterion.
- Plans to move out of the study area in the next 9 months
- There is another child in the household enrolled in the study
- Plans for significant lifestyle changes in the next 9 months (significant dietary changes while enrolled in the study)
- Participants who are eligible for the run-in period will be ineligible for randomization if they do not demonstrate adherence to run-in procedures (return diary cards with a completion rate greater than or equal to 75%)

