## 6.5 CONCOMITANT THERAPY

All drugs and/or treatments, other than specific excluded medications, are permitted while on study drug. Use of an undisclosed excluded medication will be a protocol deviation. Similarly, if a participant uses an excluded medication and the instructions in this section are not followed, the use of the excluded medication will be a study deviation. Several medications can interfere with the absorption or metabolism of vitamin D and alter 25(OH)D levels. If a participant must start on an excluded medication during the trial period (i.e. after study drug starts), the participant will discontinue study drug but will continue with all other study procedures. New medications prescribed for the control of asthma (including systemic corticosteroids used for brief time periods [less than 14 days] or change in asthma controllers) will not result in withdrawal from study drug but will be recorded. Participants will be advised not to take additional supplements containing more than 1000 international units (IU) of vitamin D per day. All concomitant medications including dates of use, formulation, dose, and frequency will be documented during the study period.

If a participant is taking over-the-counter vitamin supplement(s), study personnel will find out what supplement(s) are being taken. This will be done by showing the participants and caregivers pictures of supplements that are commonly used by the general public. If the supplement is not in the picture set, then the caregiver will be asked to bring in the bottle at the next visit. The caregiver will also be asked how frequently the supplement is taken. Once the supplement is identified, the study team can verify the dose of vitamin D that is being taken by the participant. Children will be allowed to participate if, at the initial visit, the daily dose of vitamin D is less than or equal to 1,000 IU per day.

Concomitant medications will be verified at every visit; the study team will, therefore, be able to provide on-going guidance and counseling regarding participants' daily intake of vitamin D from over-the-counter vitamins. If a study participant changes over-the-counter vitamins and the vitamin D dose changes to greater than 1,000 IU per day, the study team will ask the participant/caregiver to reduce the over-the-counter vitamin D dose to 1,000 IU per day or less. If the participant/caregiver does not follow the request

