### **Excluded medications**

- Oral or IV steroids (including prednisone and equivalent dexamethasone or other steroid dose) greater than 10 mg/day in the 30 days prior to the screening visit or during the run-in period.
  - Oral or parenteral steroids, including doses greater than 10 mg/day, may be used as an acute asthma control medicine during trial period as stated above.
- Vitamin D2 within the 30 days prior to the screening visit or during the run-in period.
- Vitamin D3 supplementation with a daily dosage of greater than 1000 IU in an individual supplement form or as part of a multivitamin within the 30 days prior to the screening visit or during the run-in period.

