## **Baseline (Visit 2, Day 0)**

Study Visit 2 must occur between 10 and 21 days, with a target of 14 days, after Study Visit 1. The goal of this visit is to review eligibility for continued enrollment, provide study procedure training, and randomize participants.

1. Interval history (concomitant medications, asthma symptoms, healthcare utilization) and diary cards (without the line to record Vitamin D dosing) will be reviewed at Visit 2 to assess eligibility for study participation.
  - a. Site must confirm that participant continues to meet inclusion/exclusion criteria except for age less than 18 years.
  - b. To be randomized, participants must complete and return diary cards with a completion rate greater than or equal to 75%. Participants who do not meet this level of adherence will be removed from the study.
2. An ACT or c-ACT will be completed by the caregiver and/or child, as appropriate.
3. Height and weight measurements for calculation of BMI and BMI-percentile.
4. Blood draw (by venipuncture) for central laboratory 25(OH)D level determination and inflammatory marker assays.
5. Study drug will be dispensed and dosing explained to the participant and his or her parent, legal guardian, or caregiver. (See Section 6.1.2).
6. Diary cards for dosing visits will be given to the participant and instructions for completion of the diary will be reviewed.
7. Study Visit 3 will be scheduled for 28 days ( $\pm 7$ ) from Study Visit 2.

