###### **1. ASDs:**

A diary card will be used to compile information about asthma symptoms. Though diary cards similar to those proposed for VDORA have been used successfully in large highly-controlled pediatric asthma trials, symptom diaries can be criticized for some participants having incomplete data. Symptom diaries however can be used successfully particularly in intervention trials less than 26 weeks (as with VDORA) and when participants are frequently reminded and supported closely by research staff. (76, 77)

An ASD (83) will be defined as a day with any one of the following:

- a. Albuterol rescue use (pre-exercise treatment permitted)
- b. Use of additional asthma medications including oral steroids. In addition, the 7 days immediately following the end of a course of oral steroids will be considered ASDs.
- c. Daytime or nighttime asthma symptoms (wheezing, coughing, phlegm/mucus, chest tightness, or shortness of breath)
- d. Unscheduled health care provider visits for asthma, emergency room visit or hospital admission for asthma, or missed work or school due to asthma

Baseline frequency of ASDs will be documented for each participant using the participant's run-in period and Week 1 (if needed) diary cards to explore changes in mean ASD/week longitudinally on treatment.

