## 2. Asthma Exacerbation

In this study an asthma exacerbation will be defined according to the recommendation of the NIH Outcomes Workshop (84) as a worsening of asthma requiring the use of a systemic corticosteroid (at least 2 days of treatment) to prevent a serious outcome. In accordance with the Expert Panel recommendations, data will be captured on the following exacerbation-related outcomes:

- a. All worsening asthma events in which systemic corticosteroids were initiated to prevent a serious outcome, including use of systemic corticosteroids in association with any form of healthcare provider encounter
- b. All asthma-specific ED or urgent care visits that involved treatment with systemic corticosteroids
- c. All asthma-specific hospitalizations that involved treatment with systemic corticosteroids (also reported as an SAE)
- d. All asthma-specific intensive care unit admissions or intubations (also reported as an SAE)
- e. All deaths (all-cause and asthma-related; also reported as an SAE)

For the purpose of this study, 2 courses of systemic corticosteroids must be separated by at least 1 week to count as 2 exacerbations and to be documented as such.

3. Episode of problematic asthma

Any asthma-related unscheduled healthcare visit (outpatient, urgent care, ED).

4. Respiratory tract infection

Patient-reported episodes of upper respiratory tract infection (cold), sore throat, strep throat, bronchitis, pneumonia, ear infection, and acute sinusitis (sinus infection) will be documented from structured interviews occurring at each study visit and planned study phone call. This approach has been used successfully in large pediatric asthma trials. (80)

---

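### Within-arm change in asthma symptom days is biased upward because the run-in baseline bars the steroid use that counts as symptom days on study, and the plan names no comparison with standard of care for the asthma outcomes

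*Combined protocol and SAP*

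**What the plan says.** **Entry.** Section 5.2 excludes "Administration of an excluded medication (systemic glucocorticoids, drugs affecting calcium metabolism, drug affecting fat absorption) within 30 days prior to study enrollment", and the wording continues "at screening (Visit 1) or at any time during the run-in period". It gives no dose threshold. The excluded-medication list in Section 6.5 is narrower, barring oral or IV steroids only when "greater than 10 mg/day in the 30 days prior to the screening visit or during the run-in period". Eligibility is checked again before randomization (Section 8.1.1.1, Visit 2): "Site must confirm that participant continues to meet inclusion/exclusion criteria except for age less than 18 years".

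**On study.** Section 6.5 lets study drug continue through new asthma medication, "including systemic corticosteroids used for brief time periods [less than 14 days] or change in asthma controllers".

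**Outcomes (Section 8.1.1.2).** An exacerbation is a "worsening of asthma requiring the use of a systemic corticosteroid (at least 2 days of treatment". ASD criterion (b) counts days with oral steroids and adds that "the 7 days immediately following the end of a course of oral steroids will be considered ASDs". Baseline ASD frequency comes from the run-in diaries, with Week 1 cards if needed, and is meant for exploring change in mean ASDs per week on treatment.

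**Analysis.** Section 9.4.10 states: "General estimating equations will be used to assess changes in the number of exacerbations, ASDs and the ACT (or c-ACT) score over time". It names no arm term, no first time point for exacerbations and no handling of steroid courses. The only between-arm test in Section 9.5 concerns the proportion reaching the 25(OH)D target.

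**The concern.** An event that contributes to the outcome is a reason for exclusion before dosing and is permitted afterwards. A measure that includes that event will tend to rise from entry whether or not vitamin D does anything.

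For ASDs this follows from the written baseline rule. For exacerbations it depends on a choice that the plan leaves open. The protocol wants these exploratory data to inform a later intervention trial (Section 2.2). An upward drift created by eligibility could mask a small benefit or be read as a small harm when each arm's change is described by itself.

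**Working it through.** The plan gives no figure for this point, so there is none to reproduce. It also gives no steroid-course rate. I assume 0.3 to 1.0 courses per child-year and a 5-day course, and vary the course length below.

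**1. What the ASD baseline can contain.** Under Section 5.2, no steroid day falls in the run-in. No 7-day tail reaches into it either, because the preceding 30 days are also steroid-free. Under Section 6.5, courses at or below 10 mg/day could remain, so the component is largely rather than wholly absent. Symptoms, albuterol use, unscheduled care and missed school or work still count, so baseline ASDs are not zero.

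**2. Upper bound on the ASD drift.** ASDs per course = course days + 7. Added ASDs per week = courses per year × ASDs per course ÷ 52.

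| Course length | ASDs per course | 0.3 per year | 1.0 per year |
|---|---|---|---|
| 5 days (assumed) | 12 | 0.3 × 12/52 = 0.07 | 1.0 × 12/52 = 0.23 |
| 2 days (minimum for an exacerbation) | 9 | 0.3 × 9/52 = 0.05 | 1.0 × 9/52 = 0.17 |

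These are upper bounds. They treat every steroid and tail day as an ASD that would not have counted otherwise, although many would already qualify through symptoms or albuterol.

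**3. Exacerbations, if a pre-dose window were used.** With 63 children and a 14-day run-in, an unselected group would have 63 × 14/365 × 0.3 = 0.7 to 63 × 14/365 × 1.0 = 2.4 courses. That is what selection removes from the run-in. The 63 × 16/52 × 0.3 = 5.8 to 63 × 16/52 × 1.0 = 19.4 courses expected over 16 weeks of dosing are mostly a matter of longer observation.

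**4. Simulation with no vitamin D effect.** Entry was restricted to children with no steroid-treated event in a 44-day window (30 days plus a 14-day run-in). Assumptions: 0.5, 1 or 2 events per child-year, gamma between-child variation with variance 1, 63 or 113 children, 2:1 allocation, 1,500 runs per setting, nominal 5% two-sided tests. A robust test of within-child change stood in for the GEE time effect.

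| Test | Rejection |
|---|---|
| Change over time, selected entry window as baseline | 95% to 100% |
| Change over time, no selection | 4.8% to 6.7% |
| Arm difference in change, with selection | 5.1% to 7.5% |

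The first row shows what would follow if that window were the first time point. The plan does not say that it is. The third row shows that the randomized contrast stays close to nominal under the same selection.

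**5. Biomarkers.** The share of Week 16 draws within 30 days of a course start is 30/365 × 0.3 = 2.5% to 30/365 × 1.0 = 8.2%. Cohort A has 63 × 2/3 = 42 children, or 42 × 0.7 = 29.4 after the planned dropout of about 30%. That gives 0.7 to 2.4 affected draws. The documents give neither sign nor size for the effect of a brief course on these markers.

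**The case against.** The strongest reply is that the plan defines a run-in baseline for ASDs only. Interval exacerbations are first listed for recording at Visit 3, and prior exacerbation history is taken at Visit 1, so the exacerbation series may already begin after dosing. A reader might infer that every child has a baseline exacerbation count of zero by rule and that the model starts from it. The documents do not support that: no exacerbation baseline is defined, and Section 6.5 bars only doses above 10 mg/day. This part of the reply stands, and the exacerbation point is conditional for that reason.

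A reader might also set 6 to 19 courses on study against none in the run-in. That compares 16 weeks with about 2.

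Third, the concurrent SoC arm has the same entry rules, so the selection is shared. This is correct, and the distortion does not carry into a randomized comparison. It does not rescue the plan as written, because exploratory objectives 1 and 2 only characterize markers and symptoms, and no arm comparison is specified for them.

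Finally, these outcomes are exploratory, Section 8.2 says this is not an asthma treatment study, and Section 9.4.1 leaves detail to a separate SAP whose text is not in the document reviewed. That limits the weight of the point. It does not change the ASD baseline rule, which the protocol already fixes.

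**Conclusion.** The point holds for ASDs. A within-arm or pooled change from the run-in is biased upward with no vitamin D effect, by at most about 0.07 to 0.23 ASD per week at the assumed 0.3 to 1.0 five-day courses per child-year. The course rate and length are assumptions, and overlap with symptom or albuterol days makes the true figure smaller.

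For exacerbations it holds only if the run-in or another pre-dose window is the first time point in the GEE, which Section 9.4.10 leaves open.

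It would go too far to say that all the asthma and cytokine results are distorted whatever vitamin D does. No such distortion is shown for the ACT, the biomarker effect has no documented direction, and the randomized contrast with SoC is not biased by this selection. The PK, Part 2 and safety endpoints are untouched. Sections 5.2 and 6.5 disagree on which steroid doses exclude a child, and the two passages must be reconciled.

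**What to change.** In Section 9.4.10 or the SAP:

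1. Model exacerbations as post-randomization counts with a follow-up-time offset. Leave the pre-dose window out, and adjust for the exacerbation history taken at Visit 1, with a stated look-back.
2. Make the arm-by-time contrast against SoC the basis for any statement about vitamin D and ASDs, exacerbations or ACT.
3. Report ASD change also without the criterion (b) steroid days and the 7-day tail, as a sensitivity analysis, so that run-in and follow-up are counted alike.
4. Optionally, flag Week 16 biomarker draws within 30 days of a systemic steroid in a descriptive sensitivity analysis, with no claim about direction.

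Medication dates, diaries and exacerbation history are already collected, so the cost is some wording and a few exploratory tables. Items 3 and 4 condition on steroid use after randomization, which treatment might influence, so they are supportive only.
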